mailed to the participant prior to this visit for self-administration and returned to the clinical site during this visit.

• *VEST Registry Follow-up Telephone Call:* Participants will be contacted by phone at least yearly to gather follow-up data. Participants will be asked about changes in medication, intervening hospitalizations, and simple follow-up questions regarding ICD/pacemaker device implantation.

Continuous Participant Monitoring (during the study period: V0-V2)

In addition to the visits described above, participants randomized to LifeVest will have continuous remote monitoring via the LifeVest.

Monitoring Capabilities and Data Collection from LifeVest: The LifeVest performs constant ECG monitoring while it is worn. It records all ventricular tachyarrhythmias that last more than 15 seconds and asystolic events (<20 beats per minute). Bradyarrhythmias (<40 bpm) are logged but no ECG is recorded. It also compiles compliance data by recording the amount of the time the LifeVest is worn each day. This data will be uploaded via modem and phone line. After initial setup, the coordinator or fitter (from ZOLL Lifecor) will upload the participant's baseline data, then the participant will upload (from home) every other day for a total of 3 times during the first week and then subsequently on a weekly basis. The DCC will notify enrolling sites if participants are not sending scheduled transmissions. The enrolling sites can then contact participants to discover problems and encourage compliance. Sites with persistent or numerous poorly compliant participants will be visited and their staff re-trained.

The participant's compliance to the visit schedule will be continuously monitored on the study website by clinical site. The CCC will review visit compliance reports with the clinical sites on the Quality Control Committee conference calls/meetings to identify problems and recommend corrective action. If a participant misses a scheduled visit, clinic staff will contact him/her immediately to review the reasons for the missed visit, to identify any barriers that can be corrected, and to reschedule the visit.

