Blinding to treatment assignment: Participants and clinicians will not be blinded to treatment assignment (LifeVest versus no LifeVest). Since the primary outcome in *VEST* is sudden death and death due to ventricular arrhythmia, it is unlikely that this outcome would be significantly affected by either participant or clinician knowledge of treatment assignment.

Blinding to arrhythmias: Clinicians will be blinded to most arrhythmia recordings from the LifeVest in the group assigned to wear the LifeVest. This is necessary to prevent co-interventions with inappropriate anti-arrhythmic drugs or early implantation of an ICD. There are provisions for unblinding when clinically indicated, as detailed in Chapter 6 of the Operations Manual. Two types of unblinding will occur:

1) Automatic unblinding, generated by the DCC or ZOLL, which will result in electronic notification to the site and sending of LifeVest monitoring strips. Automatic unblinding will be initiated if any of the following events occurs:

- Participant receives a shock
- LifeVest alarms, but participant averts a shock or the rhythm spontaneously terminates if the rhythm lasts > 30 seconds
- Asystole or Bradycardia less than 20 bpm

2) Clinical sites can request unblinding and receive LifeVest strips under the following circumstances:

- Participant suffers a cardiac arrest, or reports receiving a shock or LifeVest alarm
- Participant complains of syncope or pre-syncope
- Participant complains of palpitations
- Physician deems it to be medically necessary (a protocol deviation may be reported)

The procedure for requesting these strips will require a case report form (completed by ZOLL personnel) with a diagnosis or rationale (as outlined above), the date range of strips requested and a follow-up form that documents any treatment changes resulting from viewing these strips.

Crossovers

Participants randomized to the control arm of VEST should not wear a LifeVest during the 3 month VEST follow-up period; use of a LifeVest by a control participant will be recorded as a protocol deviation.

Treatment of Participants Who Receive a LifeVest Shock

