+ - Includes information from medical records, death certificates, interviews of next-of-kin or personal physicians, and National Death Index searches

VF - Ventricular fibrillation; VT - Ventricular tachycardia; SVT - Supraventricular tachycardia; ICD - Implantable cardioverter defibrillator

stratified by length of follow-up period (to account for the higher expected rate in patients with 90 day follow-up), and randomization stratum, as jointly defined by EF and receipt of PCI and/or CABG during the hospitalization for the index MI.

We will also conduct a secondary "modified intention-to-treat" analysis of sudden death and death due to ventricular arrhythmia, total mortality, and other secondary outcomes. For this analysis, follow-up time will start at the time of discharge instead of randomization, and end 60/90 days after discharge, and participants who are randomized but die before discharge from the index hospitalization will be excluded. For death outcomes, this analysis will use the stratified exact methods specified for the primary analysis; for more common secondary outcomes, asymptotic methods will be considered.

We will also analyze treatment effects on overall mortality and non-sudden death, non-fatal cardiovascular events, ventricular arrhythmias, adverse events, LifeVest compliance, ICD implantation, quality of life and resource utilization/cost. For rare outcomes, exact methods will be used, as for the primary endpoint. For VEST therapies and hospitalizations, we will use the Anderson-Gill extension of the Cox model for repeated events, with robust standard errors, to better capture information from high-risk participants with repeated VEST therapies or hospitalizations.

We will also conduct a secondary, "as treated" analysis of sudden death and death due to ventricular arrhythmia, total mortality, and other secondary outcomes. The primary ITT analysis will estimate effectiveness of the vest, averaged over variations in compliance. We will attempt to estimate the efficacy of the vest for prevention of sudden death and death due to ventricular arrhythmia as well as total mortality using survival models treating observed vest use as a time-dependent covariate. For sudden death and death due to ventricular arrhythmia, we will

6

Protocol

use a Fine-Gray model treating other deaths as competing risks; a standard Cox model will be used for total mortality.

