1.5.12 Sample Size Calculations

When the trial was originally designed, the sample size for the VEST study was estimated to be 1,890. This assumed a power of 80%, with a 2-sided alpha of 0.05 and a 2:1 randomization scheme. The VEST sample size was carefully computed using data-based estimates of the following factors:

1. Mortality due to sudden death in the first 2 months following an MI in patients with $EF \le 35\%$ is 2.4%. The VALIANT Study, the EPHESUS Study, and the DINAMIT Study are three recent studies reporting on mortality and sudden death rates in the early period following an MI in populations similar to our study population. A meta-analysis of these three studies populations gives a summary estimate for sudden death rate of 2.4%.

2. Mortality due to sudden death in the first 3 months following an MI in patients with $EF \le 35\%$ is 3.0%. Using month-by-month data on sudden death in VALIANT, we estimate that extending follow-up from 2 to 3 months will increase the sudden death rate by 25%, from 2.4% to 3.0%. This accounts for declines in the sudden death rate in the weeks following MI.

3. Mortality due to ventricular arrhythmias in the first 3 months following an MI in patients with $EF \le 35\%$ is 2.73%. The wearable defibrillator vest will be effective at reducing only sudden death due to a ventricular arrhythmia. The preliminary data from the wearable defibrillation vest shows that 91% of all sudden cardiac arrests are due to ventricular arrhythmias. This is consistent with estimates in the literature. *Therefore*, 91% of 3.0% would give us an expected mortality of 2.73% due to ventricular arrhythmia.

4. The effectiveness of the wearable defibrillator to reduce sudden death due to ventricular arrhythmias will be 71.9%. Previous analyses show that the LifeVest conversion success rate is 98% for syncopal VT/VF. Based on early experience in VEST and planned changes in randomization procedures, we have targeted an intention-to-treat compliance rate with the LifeVest of 70%. This means that participants assigned to the LifeVest will wear it for 70% of all hours in the 3 months following randomization, including days when the LifeVest is not worn at all. However, since compliance and event rates are both anticipated to be highest in the earliest weeks of the trial we anticipate the LifeVest will be used during more than 70% of sudden death events. Thus, we estimate that the LifeVest will reduce sudden death due to syncopal VT/VF by 71.9%.

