
5. Given the above assumptions, we estimate an overall sudden death rate of 3.0% in the control group and 1.02% in the wearable defibrillator group (67% reduction in sudden death). The absolute reduction in mortality is the mortality from ventricular arrhythmia (2.73%) times the effectiveness of the LifeVest (71.9%) = 1.98%. Thus, the sudden death rate in the defibrillator LifeVest group is expected to be the mortality in the control group minus the absolute reduction or 3.00%-1.98% = 1.02%.

6. Given the short follow-up period (3 months) and strong efforts to collect complete data, we anticipate minimal loss to follow-up and minimal crossover. Crossover in the treatment group (LifeVest group) is accounted for in #4 above (some patients will not tolerate the LifeVest). Given that the LifeVest is only available by prescription, we expect that crossover from the control group to the treatment group will be exceedingly rare.

7. A power of 80%, with a 2-sided alpha of 0.05 and a 2:1 randomization scheme. Using these estimated event rates, a 2:1 randomization scheme and the standard formula for two-group comparisons of proportions, we will need a sample of 1260 in the wearable defibrillator group and 630 in the control group, or 1890 total participants.

Updating the Sample Size for VEST: We recognized that this sample size calculation is sensitive to the values of the inputs noted above. This raises the concern that the VEST trial might fail to reach firm conclusions despite the

Protocol

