anticipated efficacy. Rates of total mortality, sudden death and death due to ventricular arrhythmia, and LifeVest compliance are especially important drivers of sample size, and these are easily monitored during follow-up. We therefore plan to update our sample size after 1000 participants have completed their VEST follow-up and then again after 1500 participants have completed follow-up. We will use interim overall rates of total mortality and sudden death and death due to ventricular arrhythmia, as well as LifeVest compliance and crossover rates (off-protocol use of the LifeVest in the NO VEST arm), in conjunction with our original assumptions about the proportion of all sudden deaths that are due to ventricular arrhythmias and the efficacy of the LifeVest in preventing these potential events. We will also account for time in the hospital after randomization but before discharge (using real estimates of time-to-discharge from the study), during which the LifeVest is typically not worn and when we expect no differential effect on mortality to be induced by assignment to VEST. Because this procedure is blinded to treatment assignment, no meaningful inflation of the type-I error rate is expected.^{11,12}

The following limits will be adhered to when updating the sample size:

- The sample size will be updated only if the revised sample size is more than 10% larger than the planned value of 1900, i.e., greater than 2100.
- The updated sample size will not exceed 4,000 (twice the current planned sample size).
- No decrease in the planned sample size will be allowed (outside of the direction of the DSMB).

FINAL SAMPLE SIZE: In October 2015, after 1500 participants completed follow-up, the VEST Data and Safety Monitoring Board (DSMB) reviewed the blinded sample size re-estimation calculations and was concerned that with the estimated power at the current sample size (n=1890) there is a substantial likelihood of type II error. Therefore, the DSMB recommended that the VEST sample size be increased in order to achieve an estimated power of at least 70%, with a composite sudden death rate in the trial of 1.66%.

On April 25, 2016, the VEST Steering Committee approved the increase in sample size to a total of 2300 participants.

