3. Inverse weighting to deal with indeterminate cause of death and missing vital status. In the primary analysis, participants with indeterminate cause of death or missing vital status will be assumed not to have had a primary study event. In two secondary analyses, we will restrict the analysis to deceased participants with determinate cause of death and those known to be alive, weighting these observations so that their baseline correlates of the primary outcome are representative of the entire randomized cohort. To do this, we will develop two logistic models: the first for having determinate cause of death among all patients known to have died, and the second for having known vital status among all participants. Weights will be calculated as the inverse of the product of the fitted probabilities from these two models, after assigning a fitted probability of 1 from the first model for patients known to be alive. Variables in each model will be selected, without regard to the primary outcome, from a list of known correlates of the primary study outcome, as specified by Drs. [name], [name], and [name]. To deal with missing values of the candidate variables in the *a priori* list, multiple imputation will be used, followed by averaging of the weights obtained from each of ten completed datasets. Two versions of this sensitivity analysis will be conducted, the first excluding and the second using information from the vest in

determining vital status. The weighted analyses will use procedures properly accounting for the slightly smaller sample size available for analysis.

B.2. Heterogeneity of treatment effects

• By randomization stratum. We will use a logistic model to assess heterogeneity of the treatment effect across the 6 randomization strata jointly defined by EF, PCI, and CABG, as well as across the 2 strata defined by EF and the 3 strata defined by PCI and CABG. Nominal differences across strata will be conservatively interpreted in the light of tests for interaction between treatment and stratum, using a Bonferroni-corrected two-sided alpha of 0.05/3=0.0167. In additional exploratory analysis, we will assess modification of the ITT treatment effect by drugs, NYHA class, BMI, gender, and compliance

B.3. Treatment effects on secondary endpoints

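### SAP B.2 treats vest compliance as a modifier of the ITT effect, but compliance is measured after randomisation and has no usable control value, so that interaction cannot be estimated

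*Combined protocol and SAP*

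**What the plan says.** After the randomisation-stratum interactions, SAP B.2 adds an exploratory step: "we will assess modification of the ITT treatment effect by drugs, NYHA class, BMI, gender, and compliance". It does not define compliance for this purpose, gives controls no value and names no method for the item.

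Elsewhere compliance means observed wear. Of the device, protocol section 1.5.4 says: "It also compiles compliance data by recording the amount of the time the LifeVest is worn each day". The sample-size target in section 1.5.12, item 4, is that participants assigned to the vest will "wear it for 70% of all hours in the 3 months following randomization, including days when the LifeVest is not worn at all". SAP B.4 models daily wear and its predictors.

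For controls, section 1.5.5 (Crossovers) says that "use of a LifeVest by a control participant will be recorded as a protocol deviation". Section 1.5.12, item 6, adds that "we expect that crossover from the control group to the treatment group will be exceedingly rare". The sample-size update in the same section counts such use as crossover.

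Protocol section 1.5.11 has a separate as-treated analysis "using survival models treating observed vest use as a time-dependent covariate". For the primary endpoint it will "use a Fine-Gray model treating other deaths as competing risks". The SAP does not contain this analysis.

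**The concern.** An ITT effect modifier has to be defined in both arms, and assignment must not affect it. NYHA class, BMI and gender at baseline meet that condition. Observed wear does not: it arises after assignment and, in practice, in one arm only. A control who obtains a vest off protocol does not show how controls would have complied if assigned one.

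The analyst would therefore probably split the vest arm by wear and compare each part with all controls. That breaks the randomisation. Death and unworn hospital days both shorten recorded wear, and wear may also be related to prognosis. An inert vest could then appear to work in those who wore it, and the SAP would report this as modification of an ITT effect. Such a claim is foreseeable, because the summary of revisions to protocol version 3.2 gives below-target wear as the reason for enlarging the trial.

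**Working it through.** The plan gives no figure for this interaction, so there is none to reproduce.

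**Inputs from the documents.** 2300 participants at 2:1; composite event rate 1.66% (section 1.5.12, final sample size); sudden death 2.4% by 2 months and 3.0% by 3 months (section 1.5.12, items 1 and 2). Expected events: 0.0166 × 2300 = 38.

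**Assumed inputs.** Wear distributions, hospital days, crossover numbers, wear–risk correlations and a person-level cut-off of 70%. The documents give none of these at person level.

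**1. Rank.** Take the columns 1, T (arm), W (wear) and T×W.
- With W = 0 in every control, T×W = W in every row: rank 3 of 4.
- With controls dropped, T = 1 and T×W = W in every row: rank 2 of 4.

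The interaction coefficient is not estimable in either case.

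**2. Crossovers.** Let 5, 10 or 20 controls wear the vest for 20–90% of hours, with vest-arm wear beta(7,3). Rank becomes 4. The median SE of the interaction log odds ratio (wear 0 to 100%) is 6.12, 4.47 and 3.34. Expected events among these controls are 5 × 0.0166 = 0.08 up to 20 × 0.0166 = 0.33. Even at SE 3.34 the 95% limits lie a factor of exp(1.96 × 3.34), about 700, either side.

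**3. High wearers against all controls, inert vest.** Two cases can be done by hand, with daily wear fixed at 0.9 and deaths uniform within days 0–60 (2.4%) and 60–90 (0.6%).
- *Share of all 90-day hours.* Reaching 70% needs 0.70 × 90 / 0.9 = 70 days alive. Deaths that qualify: 0.6% × 20/30 = 0.4%. Risk ratio = [0.004 / (0.97 + 0.004)] / 0.03 = 0.14.
- *Per hour alive, 3 unworn hospital days.* 0.9(t − 3)/t ≥ 0.7 gives t ≥ 13.5 days. Deaths lost from the high-wear group: 2.4% × 13.5/60 = 0.54%, leaving 2.46%. Risk ratio = [0.0246 / (0.97 + 0.0246)] / 0.03 = 0.82.

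Simulation with 4 million participants, several wear distributions and hospital stays of zero or exponential length gave:

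| Wear counted | Wear–risk correlation | Risk ratio, ≥70% wear v all controls |
|---|---|---|
| From discharge, both arms | 0 | 1.00 |
| From discharge, vest arm only | 0 | 0.93–1.00 |
| Per hour alive, mean 1–5 hospital days | 0 | 0.64–0.94 |
| Share of 90-day hours, no hospital days | 0 | 0.08–0.14 |
| From discharge, both arms | −0.1 to −0.3 | 0.74–0.97 |
| From discharge, both arms | −0.5 | 0.58–0.83 |
| From discharge, both arms | +0.1 to +0.3 | 1.03–1.28 |

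The selection rows use a log-risk SD of 0.5–1.0.

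**4. The alternatives.**
- *As-treated, inert vest* (day-stratified Mantel–Haenszel ratio, worn v not worn): 1.00 if wear is unrelated to risk; 0.83–0.99 with correlation −0.1 to −0.3; 0.94 or 0.76 with 5-day unworn readmissions (0.4% per day) at 3 or 10 times the hazard. Keeping other-cause deaths (4% or 8%, assumed) in the risk set with wear 0 gives 1.04 or 1.07. A full Fine–Gray fit was not run.
- *Standardised score defined in both arms:* SE per SD = √(1/e₁ + 1/e₀). With no effect, 38 events split 25 v 13: √(1/25 + 1/13) = 0.34. At the planned ratio 1.02/3.0 = 0.34 they split 15 v 23: √(1/15 + 1/23) = 0.33. The 95% limits are a factor of exp(1.96 × SE), about 1.9–2.0, either way.

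**The case against.** The item is exploratory, and B.2 says only compliance. A predicted or site-level measure is not excluded, and B.4 already models wear on site and baseline factors. But every definition in the documents is observed wear, and B.2 mentions no prediction. If a predicted score was meant, the SAP has to say so.

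The rank result belongs to one parametrisation: a model with intercept, arm and wear has full rank and can be fitted. That is correct, but its wear slope comes entirely from the vest arm. It is a non-randomised dose–response, not modification of an ITT effect.

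The most extreme ratios need a 70% person-level cut-off and a fixed 90-day denominator, and the SAP chooses neither. The documents' 70% is an arm-level target. The 0.64–0.94 range also applies full hazard in hospital, whereas SAP B.1 expects few in-hospital deaths; removing those deaths gives 0.69–0.95. Selection could run either way, since no passage says that sicker participants wear the vest less. These points stand. The sizes are therefore conditional, and the sign of selection bias is unknown.

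Daily wear and a share of all hours do not contradict each other, because one adds up to the other. What is left open is the denominator, and that choice alone moves an inert vest from about 1 to about 0.1.

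The as-treated analysis is already in the protocol, and section 2.6 commits the analysts to section 1.5.11. That does not repair B.2.

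**Conclusion.** The concern holds. Modification of the ITT effect by observed compliance cannot be estimated from this design without assumptions that the SAP does not state. That conclusion rests on the definition of wear and the near-absence of vest use in controls, not on any simulation. The risk ratios show mechanism and sensitivity under assumed inputs; they do not forecast the bias in this trial. The consequence is confined to how an exploratory result is read. The item should be corrected before analysis, but it does not threaten the main conclusion.

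**What to change.** Delete compliance from the B.2 list of ITT effect modifiers. Move the protocol's as-treated analysis into the SAP, labelled exploratory, non-randomised and open to prognostic selection. State what wear value a participant carries after death from another cause, because a Fine–Gray risk set keeps such participants.

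If effect modification by compliance is still wanted, there are two options:
- a score available in both arms, such as compliance predicted from those B.4 covariates known at randomisation; or
- a complier estimand based on assignment, with its assumptions stated and a confidence interval.

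The cost is one word deleted and one paragraph carried over, with no new data. The trial gives up an observed-compliance subgroup table. The as-treated estimate can itself be biased, and a both-arm score will be imprecise with about 38 events; the SAP should say both.

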- 2. The modified inclusion and exclusion criteria for 'PREDICTS only' are displayed in Table 1-1b on page 1-8. For participants enrolling in PREDICTS only, we broadened the inclusion criteria to include patients ≤6 months from an MI (#1, Table 1-1b). Therefore the qualifying ejection fraction (EF) is either measured during the MI hospitalization, or if the patient presents outside of the 7-day post discharge window, the "most recent EF" before enrollment is the qualifying EF (#2, Table 1-1b). This change allows for a larger pool of patients and parallels what is done in practice through application of current ICD implantation guidelines.
- 3. The modified exclusion criteria for 'PREDICTS only' excludes patients with an existing ICD, with a previous cardiac arrest, and with sustained ventricular tachycardia or ventricular fibrillation. However, patients are not excluded who have had prior CABG (after qualifying MI), paralleling current guidelines (3 months after CABG).
- 4. Page 10:Table 1-2 has been modified to reflect different tests, visits, and data collected based on the three enrollment options.
- 5. Page 14: The ICD or Reveal Implantation section was changed to allow for enrollment timing options in PREDICTS only.
- 6. Page 21-22: The bottom paragraph on page 21 and top paragraph on page 22 were modified to reflect the reduction in sample size for PREDICTS and the concurrent changes in the analysis plan.

Version 2.0 to Version 2.1 (1/29/2010)

On December 3, 2009, VEST/PREDICTS (VP) Executive and Steering Committees and the NIH appointed DSMB approved a plan to 1) change the primary outcome in VEST from all-cause mortality to sudden death and, 2) extend the follow-up time in VEST to 3 months. These changes will allow VEST to be completed with a sample size of 1900 instead of the original target of 4506, and still provide valuable information on the effectiveness of a wearable defibrillator on reducing sudden death in the post MI period.

Because this change in endpoint constitutes a departure from that which was originally reviewed, the NHLBI decided to discontinue support for VEST (they will continue support for PREDICTS) and ZOLL has agreed to provide sole support for the continuation of VEST with the above changes. The Protocol has been modified as follows:

- 1. Protocol Version change from 2.0 to 2.1
- 2. VEST Primary outcome changed from all-cause mortality to sudden death mortality
- 3. VEST follow-up changed from 2 months to 3 months

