- 9. Page 7, Section 1.5.5 Interventions in VEST, Revisions made: Participants randomized to the LifeVest will be fit with the LifeVest ideally before they are discharged from the hospital or clinic, but the fitting may occur at the participant's home within 7 days post discharge from the index MI.
- 10. Page 9, Section 1.5.6 Randomization, Revisions made: [name] replaced with "the Senior Statistician"
- 11. Page 10, Outcome Adjudication: [name] removed
- 12. Page 13, Removal of: "These rules are in accord with guidelines suggested by Gould."
- 13. Page 13, Section 1.7 VEST REGISTRY, Revisions made: In order to determine long-term outcomes in patients who are eligible and enroll to participate in VEST, all patients in the VEST Registry will have at least yearly follow-up to determine vital status, most recent EF, whether an ICD has been implanted and whether they have had any cardiovascular hospitalizations/events.
- 14. Page 15, Data Transmissions from Reading Centers, Laboratories, Removal of: "or ICD, or from a test producing digital data such as an echocardiogram, ECG, or Holter monitor"

- 15. Appendix 1.B Steering Committee: Removal of old members and additions of new members including changes to titles
- 16. Appendix 1.C Predictor Measures (selected): Removal of this appendix

Version 3.1 to Version 3.2 (June 8, 2016)

In October 2015, the VEST Data and Safety Monitoring Board (DSMB) reviewed the sample size re-estimation calculations after 1500 participants completed their Month 3 follow-up. The blinded interim analysis revealed that average LifeVest wear time was below target (i.e., below the estimated avg. of 17 hours per day, which was used for the original sample size calculations), but the composite event rate had been on target throughout the study. Due to the lower LifeVest average wear-time, which decreased the study's current estimated power, the DSMB was concerned about a substantial likelihood of type II error.

In March 2016, the DSMB recommended that the VEST sample size be increased by at least an additional 400 participants, in order to maintain adequate study power. The DSMB also recommended that VEST study investigators and staff continue intense efforts to maintain or increase the recent improvement in wear-time rates, which is also essential to achieve adequate power.

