• *Total mortality, revascularization, ICD implantation*. Treatment effects on these binary secondary endpoints will be analyzed using chi-square tests, as proposed for the primary analysis. Logistic regression will be used to adjust for baseline imbalances as needed.

• *Re-infarctions and hospitalizations*. Treatment effects on these potentially recurring outcomes will be analyzed using the Anderson-Gill extension of the Cox model for recurrent events, with robust standard errors [Therneau 2000], to account for potential clustering of recurrent outcomes within participants.

 Vest-related symptoms. Fisher's exact tests will be used to compare frequency of potentially vest-related symptoms currently tabulated in the DSMB report, including fatigue, back pain, trouble sleeping, and upper body rash and itching.

B.4. Exploratory analysis of compliance

Factors associated with compliance with the VEST will be examined in an exploratory, hypothesis- generating analysis focusing on seasonality, site, geographic region, body mass index (BMI), time on study, baseline EF, as well as age, gender, race/ethnicity, education, marital and employment status, NYHA Class, and length of hospital stay. The analysis will use two-part models for repeated daily compliance measures, the first a GEE logistic model for any use of the VEST, and the second a GEE linear model for hours of use, transformed as necessary to meet normality assumptions, for patient-days where any use is detected. Inference for the combined effects of each proposed covariate on both elements of compliance (any use and hours of use among users) will be implemented using the seemingly unrelated estimation strategy. [Weesie, 1999]

C. References

- Weesie, J. 1999. sg121: Seemingly unrelated estimation and the cluster-adjusted sandwich estimator. Stata Technical Bulletin 52: 34–47. Reprinted in Stata Technical Bulletin Reprints, vol. 9, pp. 231–248. College Station, TX: Stata Press.

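### SAP B.4 looks for site, region, season and time-on-study correlates of vest wear without naming calendar time or protocol era, so these estimates could partly reflect when participants enrolled

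*Combined protocol and SAP*

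**What the plan says.** SAP Section B.4 states that factors associated with wear "will be examined in an exploratory, hypothesis- generating analysis", "focusing on seasonality, site, geographic region, body mass index (BMI), time on study, baseline EF", followed by demographic and clinical characteristics. The model has two parts for repeated daily measures: "the first a GEE logistic model for any use of the VEST, and the second a GEE linear model for hours of use" on days with some use. The section names no date of randomization, protocol version or planned follow-up length. It does not give the working correlation, or say whether covariates enter singly or together.

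Other parts of the documents describe a trial that changed over time:

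- **Wear.** The Summary of Revisions, Version 3.1 to 3.2, reports that at the October 2015 review "average LifeVest wear time was below target (i.e., below the estimated avg. of 17 hours per day". It adds that in March 2016 the DSMB asked for efforts to "maintain or increase the recent improvement in wear-time rates".
- **Wear target.** Protocol Section 1.5.12, item 4, sets 70% wear in the light of initial trial experience and of intended changes to randomization procedures.
- **Follow-up.** The Summary of Revisions, Version 2.0 to 2.1 (1/29/2010), records "VEST follow-up changed from 2 months to 3 months". Protocol Section 1.5.11 stratifies by length of follow-up and SAP Section A assesses the outcome at 60/90 days, so the 60-day participants remain in the data.
- **Sites.** The Version 2.0 revision raised the planned number from 60 to 90. Protocol Section 1.5.3 allows slow-recruiting sites to be closed early.

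B.4 entered the SAP with Version 1.2 (12/5/2016), after the DSMB had noted the improvement.

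**The concern.** Seasonality is time of year and cannot stand in for a trend over several years. If wear rose over calendar time and a site or region enrolled mostly late, its coefficient absorbs part of that rise. A reader could then credit the site with better practice when it only enrolled later.

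Time on study has a related problem. Days 1-60 are contributed by both follow-up cohorts, and days 61-90 by the 90-day cohort alone. If the cohorts differed in wear, a pooled curve compares different people on either side of day 60.

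The stake is limited but not empty. B.4 is the SAP's only analysis of factors associated with wear, and low wear is the stated reason for raising the sample size from 1,900 to 2,300.

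**Working it through.** **The plan's own figure.** B.4 contains none. The related wear target is consistent: 0.70 × 24 h = 16.8 h per day, stated as 17.

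**Inputs from the documents.** 2,300 participants at 2:1 give 2,300 × 2/3 ≈ 1,533 in the vest arm.

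**Inputs not in the documents (assumptions).** f is the share of vest participants on 60-day follow-up, taken as 5-30%. d is mean daily wear in the later era minus the earlier era, taken as 1-4 h. The enrolment pattern by site is also assumed.

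**Site or region, with no true effect.** Spurious difference = (difference in era share) × d.
- Era shares 25 points apart, d = 1 h: 0.25 × 1 = 0.25 h.
- Sites wholly in different eras, d = 4 h: 1 × 4 = 4 h.

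**Time on study, with no true effect, independence working model.** Spurious (days 61-90 minus days 1-60) = f × d.
- f = 5%, d = 1 h: 0.05 h.
- f = 30%, d = 4 h: 1.2 h.
- If the 60-day cohort wore the vest less (d > 0), the decline is understated. If it wore it more (d < 0), the decline is overstated.

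**Simulated linear GEE.** Assumed: 1,533 participants, d = 3 h, between-person SD 5 h, within-person SD 3 h, one site type holding 80% of early and 40% of late enrollees, no true site or time effect, 8 replicates per setting.

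| f | Working correlation | Site effect, no era term | Site effect, era term | Day 61-90 effect, no era term | Day 61-90 effect, era term |
|---|---|---|---|---|---|
| 10% | independence | -0.36 h | -0.07 h | +0.24 h | -0.03 h |
| 10% | exchangeable | -0.49 h | -0.08 h | -0.02 h | -0.03 h |
| 20% | independence | -0.57 h | 0.00 h | +0.51 h | -0.04 h |
| 20% | exchangeable | -0.77 h | 0.00 h | -0.01 h | -0.04 h |

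A hand check for f = 20%, exchangeable: the early share is (0.2 × 0.8)/(0.2 × 0.8 + 0.8 × 0.4) = 0.333 in that site type and (0.2 × 0.2)/(0.2 × 0.2 + 0.8 × 0.6) = 0.077 in the other. Then (0.333 - 0.077) × 3 h = 0.77 h, which matches. The standard error of the site effect was 0.264-0.268 h without the era term and 0.271-0.274 h with it.

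**Sensitivity to the enrolment pattern (any-use part).** Assumed: participant SD 1.2 and intercept 1.5 on the logit scale, slope -0.010 per day, independence; 5-20% on 60-day follow-up with log-odds 0.5-1.0 lower; the last 25% of enrollees 0.6 higher. For a site group with no true effect:
- 45/50/55% of early/middle/late enrollees: odds ratio 1.02-1.04.
- 20/50/80%: odds ratio from about 1.13 to 1.33.
- With an era term, 0.99-1.01 in every setting.

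With 20% on 60-day follow-up and early wear 0.5 higher instead of lower, the slope per 30 days was about -0.26 against about -0.24 with the era term, so the decline was overstated.

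**Reading.** The site and region bias appears under both working correlations whenever enrolment timing differs. The time-on-study bias depends on the working correlation and changes sign with d. An era term removes both.

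**The case against.** The strongest reply is that B.4 is labelled hypothesis-generating, sits within the vest arm, feeds no test or decision, and introduces its covariates as a focus, not an exhaustive list. Nothing bars an era term. The sample-size change was settled before B.4 was written. All of this stands, and it limits the weight of the point.

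A reader might go further and infer that era differences will be reported as site or time effects. The documents do not support that. They give no enrolment pattern by site or region; the increase to 90 sites was a plan and early closure only a possibility. Season is confounded only if the seasonal pattern of enrolment differed between eras, which is not documented either.

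A reader might also infer that the decline in wear will be understated. That needs lower wear in the 60-day cohort, and no passage compares the cohorts. Section 1.5.12 sets a target and reports no direction of change. The improvement noted in 2016 came about six years after follow-up was extended, among participants who contribute both day segments. It bears mainly on site and region and says nothing about the 60-day cohort. That cohort may also be small, since the Version 2.0 revision describes early enrolment as well below expectation.

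What the reply does not remove is that wear was known to have shifted when B.4 was drafted, and that the named covariates cannot represent the shift.

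**Conclusion.** The point holds as a minor one. B.4 names no calendar-time or era term, although the documents report a late improvement in wear and plan days 61-90 only for 90-day participants. Site and region estimates could partly reflect era wherever enrolment timing differed. The time-on-study estimate could be biased in either direction under an independence working model, and hardly at all under an exchangeable one.

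The size cannot be determined. Under the assumed ranges, the spurious effect runs from 0.25 to 4 h per day for site and from 0.05 to 1.2 h per day for time on study. These figures show the mechanism and are not estimates for this trial; with similar enrolment timing across sites the site effect could be negligible. The randomized primary comparison is unaffected.

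**What to change.** In SAP Section B.4:

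1. Add date of randomization to both parts of the two-part model, as a spline or as protocol-era indicators (60-day schedule, 90-day schedule, and the period of the late wear-time effort).
2. Estimate the day 61-90 wear curve in participants on 90-day follow-up only, or adjust for planned follow-up length.
3. State the working correlation, because the time-on-study result depends on it.

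This takes a sentence or two and a date that is already collected. The cost is precision for sites that enrolled in a single era, whose effects cannot be well separated from it. In the linear simulation, where both site types enrolled in both eras, the standard error of the site effect rose only from 0.264-0.268 h to 0.271-0.274 h.
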